10.4 DESCRIPTION OF STATISTICAL METHODS

10.4.1 GENERAL APPROACH

The ZEDS trial is a multicenter double-masked RCT that will enroll approximately 780 study participants with a medical record documentation of an episode of dendriform epithelial keratitis, stromal keratitis, endothelial keratitis, and/or iritis due to Herpes Zoster that was diagnosed in the past year. Eligible study participants will be randomized via a computer IXRS system following confirmation of eligibility within PCC in 4 strata defined by age at HZO onset (less than 60 years, or 60 years and greater, at time of HZO onset) and by recent onset or chronic HZO (recent onset: HZO diagnosed within 6 months of the enrollment/ randomization visit; chronic: HZO diagnosed 6 or more months prior to the enrollment/randomization visit).

10.4.2 ANALYSIS OF THE PRIMARY EFFICACY ENDPOINT(S)

The primary endpoint is the time from randomization to development of the first occurrence of any new or worsening dendriform epithelial keratitis, stromal keratitis, endothelial keratitis, and/or iritis due to HZO, diagnosed by a change in clinical slit lamp biomicroscopy examination and accompanied by prespecified changes in treatment (see MOP) by 12 months of treatment with valacyclovir compared to placebo.

The objective of the analysis of the primary endpoint is to compare cumulative failure rates (failure defined as an episode of new or worsening dendriform epithelial keratitis, stromal keratitis, endothelial keratitis, and/or

iritis) in the valacyclovir treated groups with the placebo treated group by 12 months (treatment completion). Kaplan-Meier curves will be plotted by treatment group (overall and within strata) and 95% confidence intervals (adjusted for interim analyses) for the difference between the 12-month cumulative failure rates will be estimated (overall and within strata). Results will also be plotted within strata and by baseline disease and study participant characteristics to provide descriptive summaries of the results.

The primary study analysis will be based on a stratified log-rank (2-sided) test with adjustment for stratification factors (age, and recent onset vs. chronic disease).

Details of all analyses, including sensitivity analyses are provided in the SAP. For example, analyses will be provided that incorporate adjustments of study medication to one 500 mg pill twice daily or one 500 mg pill daily instead of the standard 2 pills daily; and that evaluate the impact of study drug discontinuation by treatment group.

10.4.3 ANALYSIS OF THE SECONDARY ENDPOINT(S)

Secondary endpoints are listed in Section 10.2 above. Methods for the analyses that compare these outcomes by randomized treatment group are described in the SAP.

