- to test the hypothesis that suppressive treatment for 12 months with oral valacyclovir 1000 mg daily reduces the incidence, severity and duration of post herpetic neuralgia (PHN) compared to placebo at 12 and 18 months in study participants with HZO.
- to test the hypotheses that vaccination against herpes zoster with the Recombinant Zoster Vaccine
 (RZV) may impact the natural history of HZO, and that suppressive antiviral treatment with
 valacyclovir 1000 mg daily compared to placebo may alter the impact of this vaccination on HZO
 activity during 12 months of study treatment.

See sections 4.2.2 for details regarding additional objectives.

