4.2.2 SECONDARY ENDPOINTS

To assess the secondary objectives, the study participants will be monitored at each visit for the following events:

- Time to development and number of episodes of new or worsening dendriform epithelial keratitis, stromal keratitis, endothelial keratitis, and/or iritis due to HZO, requiring pre-specified changes in treatment (see MOP), during the 18 months following randomization, that includes the 6 months following cessation of treatment; and during the 6 months following the end of the 12 month treatment period.
- 2. The incidence, severity, and duration of PHN at one year of treatment, and after the 6-month post-treatment follow up.
- 3. Impact of Recombinant Zoster Vaccine (RZV) vaccination on primary endpoints during 12 months of study treatment.

- 4. Development of specific manifestations of HZO, classified as dendriform epithelial keratitis, stromal keratitis (all types), endothelial keratitis, iritis requiring pre-specified changes in treatment (see MOP), neurotrophic keratopathy with or without melting and/or microbial superinfection, episcleritis, and/or scleritis during the twelve months of treatment.
- 5. Secondary glaucoma determined by IOP and treatment required.

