If the study participant decides to get the Zoster Vaccine Live (ZVL),Zostavax, manufactured by Merck) against zoster, the study medication will be discontinued one day before and resumed one month after vaccination. If the study participant gets the Recombinant Zoster Vaccine (RZV), also referred to as the herpes zoster subunit vaccine (Shingrix manufactured by Glaxo Smith Kline), the study medication is to be continued. As of January, 2018 the CDC recommends the RZV as preferred over ZVL.

Temporary or Permanent Discontinuation due to Use of Open Label Oral Valacyclovir, Acyclovir or Famciclovir Treatment for Other Conditions

- If the study participant develops ocular, orofacial, or genital HSV disease and requires a short term (maximum two weeks) course of oral antiviral treatment, the study medication will be temporarily discontinued during this treatment, and resumed afterwards. If the study participant requires longterm antiviral treatment for HSV, the study medication will be permanently discontinued, the participant will continue to be followed in the study, and the study medication will not be unmasked.
- If study participant develops HZ in another anatomical location, study medication will be discontinued, the participant will be given recommended acute antiviral treatment for 7 days, and then the study medication will be resumed.
- If study participant is diagnosed with central nervous system disease (including stroke) due to zoster, study medication will be discontinued while participant receives intravenous antiviral treatment, sometimes followed by a course of oral antiviral treatment, and resumed afterwards, if the treating neurologist agrees. The study participant will continue to be followed in the study.
- If study participant develops any other medical condition that necessitates treatment with valacyclovir, acyclovir, or famciclovir, the study medication will be discontinued while on open label treatment and resumed afterwards,. The open label treatment period should not usually exceed two weeks.

Temporary Discontinuation due to Short-term (maximum two weeks) Open Label Use of Valacyclovir, Acyclovir or Famciclovir for HZO

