10.2 STATISTICAL HYPOTHESES

The primary objective of this randomized controlled clinical trial is to test the hypothesis that long-term suppressive antiviral treatment for 1 year with oral valacyclovir 1000 mg daily delays the time to the first occurrence of new or worsening anterior segment ocular disease (*dendriform epithelial keratitis*, *stromal keratitis*, *endothelial keratitis*, *and/or iritis*) compared to placebo by 12 months.

The secondary objectives are (1) a) to test the hypothesis that long-term suppressive antiviral treatment for 1 year with oral valacyclovir 1000 mg daily delays the time to the first occurrence of new or worsening anterior segment ocular disease (*dendriform epithelial keratitis, stromal keratitis, endothelial keratitis, and/or iritis*) compared to placebo by 18 months; and b) to test the hypothesis that the occurrence of new or worsening disease in the 6 months post treatment period is reduced for participants treated with valacyclovir compared to placebo; and (2) to test the hypothesis that suppressive treatment for 12 months with oral valacyclovir 1000 mg daily reduces the

incidence, severity and duration of post herpetic neuralgia (PHN) compared to placebo at 12 and 18 months in patients with HZO.

To evaluate these hypotheses, the following endpoints will be evaluated:

Primary Efficacy Endpoint:

The primary endpoint is the time to first occurrence of new or worsening episode of dendriform epithelial keratitis, stromal keratitis, endothelial keratitis, and/or iritis due to HZO, accompanied by pre-specified changes in treatment for the same disease manifestation of HZO (see MOP) during the twelve months of treatment. The primary endpoint is compared for participants randomized to study medication or placebo.

To assess the primary objectives, study participants will be monitored at each visit for new or worsening any of the following conditions (see MOP for definitions):

- 1. Dendriform epithelial keratitis:
- 2. Stromal keratitis
 - a. Without ulceration
 - b. With ulceration
- 3. Endothelial keratitis
- 4. Iritis

The endpoint of first occurrence of new or worsening dendriform epithelial keratitis, stromal keratitis, endothelial keratitis, and/or iritis will be determined by clinical examination accompanied by prespecified changes in treatment (see MOP), as there are no validated confirmatory biomarkers or other tests.

Secondary Efficacy Endpoints:

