To assess the secondary objectives, the study participants will be monitored at each visit for the following:

- Time to development and number of episodes of new or worsening dendriform epithelial keratitis, stromal keratitis, endothelial keratitis, and/or iritis due to HZO, requiring pre-specified changes in treatment (see MOP), during the 18 months following randomization, that includes the 6 months following cessation of treatment; and during the 6 months following the end of the 12 month treatment period.
- 2. The incidence, severity, and duration of PHN at one year of treatment, and after the 6 month post-treatment follow up.
- 3. Impact of vaccination against zoster with RZV on outcomes.
- 4. Development of specific manifestations of HZO, classified as dendriform epithelial keratitis, stromal keratitis (all types), endothelial keratitis, iritis requiring pre-specified changes in treatment (see MOP), neurotrophic keratopathy with or without melting and/or microbial superinfection, episcleritis, and/or scleritis during the twelve months of treatment.
- 5. Secondary glaucoma as determined by IOP and treatment required.

Exploratory Efficacy Endpoints:

- 1. Changes in strength and/or frequency of prescribed topical corticosteroids at 12 and 18 months.
- 2. Occurrence of stroke
- 3. Occurrence of temporal arteritis/giant cell arteritis
- 4. Occurrence of myocardial infarction

- 5. Occurrence of new or worsening malignancy
 - a. Solid tumor (other than non-melanoma skin cancer)
 - b. Hematologic malignancy
 - c. Lymphoma.
- 6. Time to development and number of episodes of new or worsening dendriform epithelial keratitis, stromal keratitis, endothelial keratitis, and/or iritis due to HZO, with a recent substantial reduction in treatment (see MOP) during 12 months of treatment.
- 7. Impact of suppressive antiviral treatment prior to enrollment on outcomes during 12 months of study treatment.

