10.4.9 ADDITIONAL SUB-GROUP ANALYSES

Analyses of primary and secondary endpoints will be presented by strata, by covariates including comorbidities such as diabetes, cancer among others, and by Zoster vaccination status as well as by gender. Details are provided in the SAP. Pre-specified subgroup analyses will be provided in the SAP.

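### Does Section 10.4.3 commit the recombinant zoster vaccine objective to a comparison that cannot answer it?

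*Combined protocol and SAP*

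**What the plan says.** Section 3 lists among the secondary objectives "to test the hypotheses that vaccination against herpes zoster with the Recombinant Zoster Vaccine" may affect the natural history of HZO, and that valacyclovir compared with placebo may alter that effect during the 12 months of treatment. Section 4.2.2 makes this secondary endpoint 3: "Impact of Recombinant Zoster Vaccine (RZV) vaccination on primary endpoints during 12 months of study treatment".

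Section 10.2 gives a shorter list of secondary objectives. The first covers the 18-month and post-treatment ocular outcomes. The second and last begins "and (2) to test the hypothesis that suppressive treatment for 12 months with oral valacyclovir 1000 mg daily reduces the" and goes on to postherpetic neuralgia (PHN). RZV is not mentioned there. The endpoint list follows, introduced by "To evaluate these hypotheses, the following endpoints will be evaluated", and its third secondary item is "Impact of vaccination against zoster with RZV on outcomes", with no endpoint or period named.

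Section 10.4.3 refers back to the 10.2 endpoints and adds: "Methods for the analyses that compare these outcomes by randomized treatment group are described in the SAP". Section 10.4.9 says that primary and secondary endpoints will also be presented "by Zoster vaccination status as well as by gender", with details in the SAP. Section 10.1 makes the SAP the full description of the analyses. The SAP text was not among the material examined here.

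**The concern.** Three things look wrong together.

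- **Status.** Section 3 says the RZV hypotheses are to be tested. The 10.2 objectives omit them, yet the endpoint list that is meant to serve those objectives includes RZV. One could fear that RZV's standing would be settled once results are known.
- **Comparison.** Secondary endpoints 1, 2, 4 and 5 are outcomes and can be compared between arms. Item 3 is the effect of an exposure that is not randomized. The first hypothesis needs vaccinated against unvaccinated participants. The second needs a treatment-by-vaccination interaction. Read literally, 10.4.3 offers neither.
- **Exposure.** The vaccination split in 10.4.9 is not limited to RZV, although Section 6.1.8 treats the two vaccines differently. For the live vaccine, "the study medication will be discontinued one day before and resumed one month after vaccination"; with RZV, study medication goes on.

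If all this held, a named secondary objective would get an answer to a different question.

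**Working it through.** **The plan's own figures.** Section 10.5 gives about 390 per arm, 12-month failure of 30% and 21.3%, two-sided alpha 0.05, 80% power and a hazard ratio of 0.67.

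- Hazard ratio: ln(1 − 0.213) / ln(1 − 0.30) = 0.2395 / 0.3567 = 0.672.
- Two-proportion sample size (pooled variance): 395 per arm; power at 390 per arm is 79.6%.
- Expected events: 390 × 0.30 + 390 × 0.213 = 117.0 + 83.1 = 200.1. Log-rank power at 0.67 is 80.8%.

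These agree with Section 10.5. No figure is stated for either RZV hypothesis.

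**What an overall by-arm contrast would show.** Suppose a share v is vaccinated before randomization in both arms, with RZV hazard ratio h and no interaction (v and h are assumed). Failure is v(1 − 0.70^h) + (1 − v)(0.30) on placebo and v(1 − 0.787^h) + (1 − v)(0.213) on valacyclovir. For v = 0.5 and h = 0.5:

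- placebo: 0.5 × 0.1633 + 0.5 × 0.30 = 0.2317
- valacyclovir: 0.5 × 0.1129 + 0.5 × 0.213 = 0.1629
- ratio of cumulative hazards: ln(0.8371) / ln(0.7683) = 0.675

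Over h = 0.5, 0.67, 1.0 and 1.5 and v from 10% to 90%, the by-arm hazard ratio runs from 0.672 to 0.675. That contrast therefore carries essentially no information on the first hypothesis. This follows almost by construction, because uptake was set equal in the two arms.

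**Whether the plan prescribes that contrast.** Reading the sections together:

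1. Section 10.4.3 is a single cross-reference. It names no test, model or estimate and does not exclude other comparisons.
2. Item 3 is the impact of RZV. Comparing that impact between arms is the second hypothesis of Section 3. The flat 0.67 appears only if item 3 is replaced by the primary endpoint itself.
3. Section 10.4.9 supplies treatment results by vaccination status, which are the ingredients for the interaction.
4. RZV is called secondary in Sections 3, 4.2.2 and 10.2 and exploratory nowhere. Secondary endpoints 4 and 5 (specific manifestations, glaucoma) also have no matching objective in 10.2, so that list is abbreviated in general.
5. Section 10.4.10 says that any multiplicity adjustment for secondary analyses goes into the SAP before unmasking.

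**What precision is available.** With D = 200.1 events and share v vaccinated (fixed status, no confounding), power for a hazard ratio of 0.67 is Φ(√(D v(1 − v)) × 0.4005 − 1.96). For a ratio of hazard ratios of 0.67, the square root is halved.

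| v (assumed) | RZV effect, 0.67 | Interaction, 0.67 |
|---|---|---|
| 10% | 40% | 13% |
| 20% | 62% | 20% |
| 30% | 74% | 25% |
| 50% | 81% | 29% |

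The interaction would be imprecise, but the protocol claims no power for it, and wording would not alter these figures.

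**Pooling the vaccines.** If 25%, 50% or 75% of vaccinations were the live vaccine with no effect, a true RZV hazard ratio of 0.67 would read about 0.75, 0.83 or 0.91 on placebo. Neither those shares nor the null effect has a source in the documents. Item 3 names RZV in both 4.2.2 and 10.2, and nothing says that the broader label in 10.4.9 defines the RZV analysis. Section 6.1.8 also records that RZV has been the preferred vaccine since January 2018.

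**The case for a change.** The strongest case for a change is that the SAP cannot cure a disagreement between two parts of the protocol. Section 3 sets two hypotheses, and the 10.2 objectives contain neither. If the SAP holds a proper RZV model, 10.4.3 describes it badly for item 3. Vaccination is the participant's choice and can come before entry or during treatment, so the analysis needs a defined exposure time, protection against immortal-time bias and adjustment for confounding. None of this is visible in the protocol, and putting it in writing before unmasking would cost little.

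Part of this stands. The 10.2 objectives do omit RZV. Item 3 is worded more loosely in 10.2 than in 4.2.2. The by-arm phrase in 10.4.3 does not describe the contrast needed for the first hypothesis.

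The rest does not carry. Exposure timing, time-dependent handling and adjustment are details that belong in the SAP, to which the protocol expressly defers. Their absence from a cross-reference does not show that they are missing. Table 1 has no vaccination row, but Section 4.2.2 says participants are monitored at each visit for the listed items, and the forms and the Manual of Procedures were not examined. No inference about unrecorded vaccination is possible.

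**Conclusion.** The concern does not hold as a defect in the analysis. It treats a pointer to the SAP as an analysis rule. The statement that the by-arm comparison returns 0.67 whatever RZV does is correct only for an overall contrast used to answer the first hypothesis, and the protocol does not say that this will be done. Sections 3 and 4.2.2 fix the vaccine, the primary endpoint, the 12-month period and the modification by treatment. A statistician working from them would estimate a vaccinated-versus-unvaccinated hazard ratio and a treatment-by-RZV interaction and report both as observational.

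What is left is a clerical mismatch between 10.2 and Sections 3 and 4.2.2, and detail left to the SAP. RZV's secondary status is consistent wherever it is named. The primary comparison, the sample size and the other secondary endpoints are unaffected, and the low interaction power (at most 29% for a ratio of 0.67) contradicts no stated figure. The vaccine uptake, timing and live-vaccine shares used above are assumptions, because the documents give none. The conclusion also rests on the SAP doing what Section 10.1 says it does.

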10.4.4 EXPLORATORY ANALYSES

Exploratory analyses to compare the rates of occurrence of each of the exploratory endpoints described above will be conducted as described in the SAP.

10.4.5 SAFETY ANALYSES

All study participants who were randomized into the study will comprise the intent-to-treat population, the primary analysis population for efficacy. Study participants who received at least one dose of the assigned study drug will comprise the as-treated population, the primary analysis dataset for safety.

The analysis datasets for safety are described in Section 10.3 (Analysis Datasets) above. Details are provided in SAP.

The occurrence of acute kidney failure, defined as requiring temporary or permanent dialysis, in these patients will be monitored using a safety monitoring rule as described in the SAP and compared between the two treatment groups.

SAEs will be analyzed in a similar manner. For all safety events, the rates of study drug termination will be summarized and compared by treatment group and strata.

10.4.6 ADHERENCE AND RETENTION ANALYSES

Study recruitment, retention, and adherence will be monitored by PCC and randomization strata. For each PCC, numbers of patients screened, numbers randomized, numbers of ineligible patients, treatment compliance as measured by pill count for individual study participants, protocol deviations, timeliness of data reporting and query resolution, numbers of queries/study participant, and additional monitoring measures will

be provided by center and reviewed monthly. All results will be summarized over time using descriptive statistics, graphical displays, and frequency distributions as appropriate. Retention rates by PCC and strata will also be monitored over time.

10.4.7 BASELINE DESCRIPTIVE STATISTICS

Plans for the comparison of baseline characteristics between the two randomized treatment groups are provided in the SAP.

10.4.8 PLANNED INTERIM ANALYSES

The interim analysis plan is described in the SAP.

10.4.8.1 SAFETY REVIEW

For ethical reasons, an independent DSMC appointed by the National Eye Institute (NEI), will monitor study participant safety and review performance of the trial at regular intervals during the trial. The primary objective of these interim safety analyses is to ensure the safety of the study participants randomized in the trial. This interim monitoring will involve a review of study participant recruitment, compliance with the study protocol, status of data collection, and other factors that reflect the overall progress and integrity of the study. Formal interim analysis of efficacy will evaluate the accumulating endpoint data by treatment group. The interim monitoring plan is described in the SAP.

10.4.8.2 EFFICACY REVIEW

Interim analysis(es) for efficacy by treatment group will focus on the primary endpoint is described in the SAP.

Judgment concerning the continuation of the study will involve not only the magnitude of observed differences between randomized strategies and degree of statistical significance, but also careful consideration of many other important factors including the need for precise parameter estimation, the overall progress and integrity of the trial including the frequency of serious adverse events associated with active study medication, and information available from other studies at the time of DSMC deliberations.

10.4.9 ADDITIONAL SUB-GROUP ANALYSES

Analyses of primary and secondary endpoints will be presented by strata, by covariates including comorbidities such as diabetes, cancer among others, and by Zoster vaccination status as well as by gender. Details are provided in the SAP. Pre-specified subgroup analyses will be provided in the SAP.

10.4.10 MULTIPLE COMPARISON/MULTIPLICITY

A statistical adjustment for interim efficacy analyses is incorporated into for the analysis of the primary endpoint. No further adjustments for multiplicity are incorporated; any adjustments for multiplicity developed for the secondary analyses for the final study protocol will be incorporated into the SAP prior to unmasking and analysis of results.

